159 session. All staff will be required to demonstrate competence in pessary placement on a live
160 model.

161 Women in the control group will receive the same obstetrical care as those in the study group.
162 All the participants will be followed in outpatient settings every month until delivery. In the
163 pessary group, a digital exam will be done at each of these monthly visits to assure proper
164 pessary placement. At any follow-up visit, TVU CL and assessment of adverse events will be
165 recorded. For TVU CL ≤ 20 mm, women in both groups will be all recommended vaginal
166 progesterone 200mg suppositories daily until 36 6/7 weeks.

167 No bed rest or activity restriction will be recommended. Abstain from vaginal intercourse will
168 also not recommended.

169 In the study group, the Arabin pessary will be placed at the time of randomization and will be
170 removed during the 37th weeks (37 0/7 – 37 6/7) or early if clinically indicated. Reason for early
171 removal includes active vaginal bleeding, preterm labor with persistent contractions and
172 advanced dilatation despite tocolysis, severe discomfort, or subject request.

173 **RANDOMIZATION AND MASKING**

174 After written informed consented will be obtained from the eligible participants, women will be
175 randomly allocated in a 1:1 ratio to either the pessary group or control group. Women were
176 randomized by a web-based system (randomization.com) using random blocks of 2,4 and 6 to
177 receive the pessary or no pessary. Randomization will be stratified by CL (CL \leq 20mm, CL
178 $>$ 20mm – 25mm).

179 The randomization sequence will be prepared by an independent statistician (at Division of
180 Statistics, Department of Law, Economics, Management and Quantitative Methods, University of
181 Sannio, Benevento, Italy) and implemented by use of central telephone. The recruiters or the trial
182 coordinator will not have access to the randomization sequence. The allocation code will not be
183 disclosed after the patient's initials are confirmed. The study will be open label because of the
184 nature of the intervention, but the outcome assessors, data collectors, and data analysts will
185 blinded to the allocated treatment group.

186 **PRIMARY AND SECONDARY OUTCOMES**

187 The primary outcome is SPTB $<$ 34 weeks

188 The secondary outcomes are:

189 - SPTB $<$ 37, $<$ 32, and $<$ 28 weeks

- 190 - Mean gestational age at delivery in weeks

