- 191 - Mean latency in days (time from randomization to delivery)
- 192 - PPROM <34 weeks
- 193 - Mode of delivery
- 194 - Maternal side effects
- 195 - Chorioamnionitis (i.e. inflammation of the chorion and amnion by histopathological
- 196 assessment after delivery)
- 197 - Birth weight
- 198 - NICU
- 199 - Neonatal death (i.e. death of a live-born baby within the first 28days of life)
- 200 - Perinatal death (either fetal or neonatal mortality)
- 201 - A composite of adverse perinatal outcome defined as at least one of the following:
 - 202 ○ NEC
 - 203 ○ IVH grade 3 or higher
 - 204 ○ RDS
 - 205 ○ BPD
 - 206 ○ ROP requiring therapy
 - 207 ○ Blood-culture proven sepsis
 - 208 ○ Neonatal death.

209 **SAMPLE SIZE**

210 The sample size calculation presented here is based on detecting an effect that produces 50%
211 reduction in the overall incidence of spontaneous preterm delivery between randomization and

212 33 6/7 weeks from an anticipated 25% in the control group (i.e. singletons with short cervix with
213 vaginal progesterone).

214 On the assumption that 60% of women with singleton gestations fulfilling the entry criteria agree
215 to participate in the study and provide follow-up data, we would be to approach about 500 such
216 women for a final sample size of 300 women. The power calculations of 300 women (150 per
217 group) were undertaken by computer simulation.

218 At our institution, we perform about 3,000 deliveries per year. However, our hospital is the one
219 of the few referral center in the Regione Campania (an area of about 55,000 deliveries per year)
220 for PTB and most of the women with short TVU CL at the routine anatomy scan are referred to
221 our institution. Therefore, we perform about 600 counselling per year on the risk of PTB in
222 singleton gestations with short cervix, of them about 500 are singleton gestations without prior
223 SPTB. Based on these data, we estimate a 2-year study period, 1 year for enrollment and 1 year
224 for data analysis.

225 **STATISTICAL ANALYSIS AND REPORTING**

226 Results will be presented according to the CONSORT statement.

227 ***Baseline data***

228 Baseline data on (LIST) for the intervention and control groups will be summarized for by the
229 median and the interquartile range. Continuous data will be summarized in terms of mean, SD,
230 minimum, maximum, and quartiles. Attribute data will be summarized on terms of frequency
231 counts and proportions

232 ***Primary analysis***

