233 The primary analysis will be an intention to treat comparison of the treatment assigned at
234 randomization. The treatment effect will be tested at the two-tailed 5% level. A 95% CI will be
235 produced the OR of intervention/control group. The incidence of SPTB <34 weeks will
236 quantified by the OR with 95% CI using the logistic regression allowing for cervical length as a
237 covariate

238 *Secondary analysis*

239 The risk of SPTB <34 will be assessed with the use of Kaplan-Meier analysis, in which
240 gestational age is the time scale and spontaneous delivery the event, and elective deliveries will
241 be treated as censored. Hazard ratios will be estimated.

242 Statistical analysis will be performed using Statistical Package for Social Sciences (SPSS) (IBM
243 Inc., Armonk, NY, USA)

244 **REGULATORY ISSUES**

245 This study is approved by the local IRB at University of Naples Federico II (Comitato Etico
246 Carlo Romano) (Unina trial #213/15)

247 **FUNDING**

248 No financial support will be received for this study

249

250

251

252 **REFERENCES**

254 items for trials. *Int J Surg*, 2015; 13:288-91

255 Altman DG. *Practical statistics for medical research*. London: Chapman and Hall, 1991

256 Berghella V, Ludmir J, Simonazzi G, Owen J. Transvaginal cervical cerclage: evidence for
257 perioperative management strategies. *Am J Obstet Gynecol*, 2013; 209:181-92

258 Berghella V, Odibo AO, To MS, Rust OA, Althuisius SM. Cerclage for short cervix on
259 ultrasonography: meta-analysis of trials using individual patient-level data. *Obstet Gynecol*,
260 2005; 106:181-9

262 *Rep*, 2012; 61:1-20

263 Khalifeh A, Berghella V. Universal cervical length screening in singleton gestations without
264 a previous preterm birth: ten reasons why it should be implemented. *Am J Obstet Gynecol*,
265 2015 Dec 19. Doi: 10.1016/j.ajog.2015.12.017

266 Miller ES, Grobman WA, Fonseca L, Robinson BK. Indomethacin and antibiotics in
267 examination-indicated cerclage: a randomized controlled trial. *Obstet Gynecol*, 2014;
268 123:1311-6

269 Roman et al. Cerclage in twin pregnancy with dilated cervix between 16 to 24 weeks of
270 gestation: retrospective cohort study. *Am J Obstet Gynecol*. 2016 Jul;215(1):98.e1-98.e11.
271 doi: 10.1016/j.ajog.2016.01.172. Epub 2016 Jan 28.

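### Gestational age at randomisation is named in no stated treatment comparison; adding it is a small, nearly free efficiency gain, mainly for latency

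*Protocol*

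**What the plan says.** - **Entry window.** The Summary table of the protocol allows randomisation from 18 0/7 to 23 6/7 weeks.
- **Stratification.** Randomization and masking stratifies by cervical length only, in two bands (up to 20 mm, and above 20 to 25 mm).
- **Event window.** Sample size aims at a 50% "reduction in the overall incidence of spontaneous preterm delivery between randomization and" 33 6/7 weeks, from an anticipated 25% in controls. "The power calculations of 300 women (150 per" group) are said to rest on simulation. No power figure is given.
- **Primary model.** Under Primary analysis, the incidence of SPTB <34 weeks is "quantified by the OR with 95% CI using the logistic regression allowing for cervical length as a" covariate. No other covariate is named. "The treatment effect will be tested at the two-tailed 5% level".
- **Secondary outcomes.** The list contains mean gestational age at delivery and "Mean latency in days (time from randomization to delivery"). No analysis method is stated for either.
- **Time-to-event analysis.** Secondary analysis sets out a Kaplan-Meier analysis and hazard ratios with gestational age as the time scale. It does not say when a woman enters the risk set.

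**The concern.** Gestational age at randomisation is known for every woman, because eligibility and latency both need it. It fixes how long each woman can have a primary event, and it is an arithmetic part of latency. A baseline variable with that standing would normally be used in the analysis, but no stated comparison names it.

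The stake is efficiency and consistency, not validity. With power near 80% for the design effect, a little extra power is worth having if it costs nothing. For latency, a chance difference between the arms in entry age would appear, day for day, as a difference in the outcome.

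**Working it through.** **1. The plan's own sample size.** The inputs are 25% against 12.5%, two-sided 5%, and 150 per arm (Sample size; Primary analysis).
- Pooled risk = 0.1875. Null SE = √(2 × 0.1875 × 0.8125 / 150) = 0.0451. SE under the alternative = √((0.1875 + 0.1094) / 150) = 0.0445.
- Power = Φ((0.125 − 1.96 × 0.0451) / 0.0445) = Φ(0.824) = 79.5%. A power of 80% needs 152 per arm, so 300 is reproduced if 80% was intended (an assumption).
- Expected events = 150 × 0.25 + 150 × 0.125 = 56.25.

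**2. Time at risk.** In days, 18 0/7 = 126, 23 6/7 = 167 and 34 0/7 = 238. The entry spread is 167 − 126 = 41 days. Time at risk runs from 112 days (16.0 weeks) down to 71 days (10.1 weeks).

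**3. A plausible association with the primary outcome.** The protocol gives none. As an illustration, take a constant hazard that yields 25% over 13 weeks: h = −ln(0.75)/13 = 0.0221 per week. Risk is then 19.9% over 10 weeks and 29.8% over 16 weeks. The odds ratio per later week of entry is [(0.199/0.801)/(0.298/0.702)]^(1/6) ≈ 0.91, or about 1.1 per earlier week.

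**4. Power for the primary outcome, by simulation.** There are 150 women per arm with marginal risks of 25% and 12.5%. Set A has 8,000 trials per row, cervical length uniform on 8–25 mm with odds ratio 1.08 per mm, uniform entry, and a likelihood-ratio test. Set B has 4,000 trials per row, cervical length about normal (mean 19, SD 5 mm) with log odds ratio −0.06 per mm, uniform entry, and a Wald test.

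| Set | Odds ratio per earlier week | Power, cervical length only | Power, plus entry age |
|---|---|---|---|
| A | 1.0 | 80.8% | 80.7% |
| A | 1.1 | 80.8% | 81.2% |
| A | 1.3 | 80.5% | 81.8% |
| A | 1.5 | 81.0% | 83.2% |
| B | 1.0 | 79.6% | 79.3% |
| B | 1.11 (1/0.9) | 79.8% | 80.3% |
| B | 1.25 (1/0.8) | 80.5% | 81.0% |
| B | 1.43 (1/0.7) | 80.5% | 82.1% |

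With entry clustered near 21 weeks (SD 1.2 weeks), the largest gain in Set B falls to 1.0 point. Type I error in Set A is 4.6% under both models.

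The gain does not come from a narrower standard error. In Set B the mean SE of the log odds ratio rises from 0.318 to 0.320 at 0.9 per later week, and from 0.317 to 0.327 at 0.7. What grows is the conditional treatment effect: its odds ratio is 0.424 when entry age has no effect and 0.406 at 0.7 per later week.

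**5. Latency: chance imbalance.** If entry is uniform over 41 days, its SD is 41/√12 = 11.84 days. The SE of the difference in mean entry age is 11.84 × √(2/150) = 1.37 days, so the 95% range is ±2.7 days. With an entry SD of 7 days it is 1.96 × 7 × √(2/150) = ±1.6 days.

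**6. Latency: variance.** Let latency be D − E, with D the gestational age at delivery (SD s), E the gestational age at entry (SD e), and r their correlation.
- Unadjusted variance = s² + e² − 2rse. Adjusted for E, it is s²(1 − r²).
- The difference is (e − rs)², which cannot be negative.

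The delivery SDs below are assumptions.

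| Entry SD (days) | r | s = 21 days | s = 28 days | s = 35 days |
|---|---|---|---|---|
| 11.84 | 0 | 24.1% | 15.2% | 10.3% |
| 11.84 | 0.2 | 12.1% | 4.9% | 1.9% |
| 7 | 0 | 10.0% | 5.9% | 3.8% |
| 7 | 0.2 | 1.8% | 0.3% | 0.0% |

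For example, the first cell is 140.1/(441 + 140.1) = 24.1%. A smaller delivery SD would give more: 17.5 days at r = 0 gives 140.1/(306.3 + 140.1) = 31%.

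**7. Latency and gestational age at delivery.** If D = a + bT + cL + dE + error, with T treatment and L cervical length, then D − E = a + bT + cL + (d − 1)E + error. The treatment coefficient b is the same. Unadjusted, the two listed outcomes differ by exactly the chance difference in entry age.

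**The case against.** The strongest reply is that nothing here is wrong. The protocol prespecifies an intention-to-treat logistic model that adjusts for the variable used to stratify randomisation. Randomisation keeps that comparison valid, and ordinary standard errors already allow for chance imbalance in entry age. This stands, and it makes the point a suggestion.

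The gain on the primary outcome is also close to nil where the association is plausible. Odds ratios of 1.3 or 1.5 per earlier week compound over the 5.86-week window to about 4.7 or 10.8, and nothing in the protocol supports values that large. This stands too.

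On latency, women are referred after the routine anatomy scan, so entry ages may cluster, and the 24% is a favourable corner. The two benefits are also largely alternatives: if early entry predicts early delivery, the primary analysis gains and latency gains less. Moreover, the adjusted latency effect is the adjusted effect on gestational age at delivery, which is already a listed outcome, so the trial learns little that is new. All of this limits the size. What remains is that adjustment removes an avoidable disagreement between two listed outcomes.

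Three stronger readings are tempting, and the protocol does not support them:
- **That the primary analysis throws away precision.** In a logistic model the added covariate does not narrow the SE of the log odds ratio.
- **That latency will be compared by plain means.** No method is stated, and one may stand in an analysis plan that is not shown.
- **That entry age is ignored everywhere.** The hazard-ratio analysis already runs on the gestational-age scale. What is unstated there is the entry time.

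**Conclusion.** The point holds as a minor, optional improvement. No stated treatment comparison names gestational age at randomisation, although it sets a time at risk of 16.0 to 10.1 weeks and forms part of latency.

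- **Primary outcome:** about 0 to 0.5 power points at a plausible association, and about 1 to 2 points only if entry age is strongly prognostic. If it is not prognostic at all, the simulations show a change of −0.1 to −0.3 points. Differences of a few tenths are within simulation error.
- **Latency:** chance imbalance of up to ±2.7 days (uniform entry) no longer passes into the result, the estimate agrees with that for gestational age at delivery, and about 0% to 24% of the variance is removed.
- **Time-to-event analysis:** on a gestational-age scale a woman is at risk only from her own entry. Counting her earlier would overfill the risk sets before 23 6/7 weeks; after that every woman has entered.

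These sizes rest on assumed entry distributions, delivery SDs of 21 to 35 days, correlations of 0 to 0.2, and assumed odds ratios per week. A reader should not infer bias or an invalid test from them.

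**What to change.** Before the data are analysed, state the following under Statistical analysis and reporting:
- *Primary analysis:* logistic regression of SPTB <34 weeks on treatment, cervical length at randomisation and gestational age at randomisation (in days, linear).
- *Latency:* linear regression on treatment with the same two covariates. If gestational age at delivery is analysed in the same way, the two treatment estimates coincide.
- *Time-to-event analysis:* on the gestational-age scale, each woman enters the risk set at her gestational age at randomisation (delayed entry). Confirm that the chosen software accepts an entry time.

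This takes a few lines of text and no new data, visits or patients. Statistically it costs one extra parameter against about 56 expected events, with a trivial loss of power if entry age turns out not to be prognostic. The primary odds ratio becomes conditional on entry age as well as on cervical length, and the report should say so.
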